For example, to assess the effects of memantine on "gating" measures in schizophrenia patients, the primary measure will be evaluated by 2-way repeated-measure ANOVA of PPI with memantine dose and prepulse interval as within-subject factors. The hypothesis that memantine will increase PPI in schizophrenia patients will be confirmed by a significant effect of dose (active > PBO) or significant dose x interval (int) interaction and post-hoc comparisons at one or more prepulse intervals. Existing data (see above) provide a strong *a priori* prediction that the 120 ms prepulse interval will be most sensitive to PPI-enhancing effects of MEM. The effect size (d) for PPI-enhancement by 20 mg memantine in HCS was 0.91; with a similar "d" in patients, 30 patients/dose yields power of 0.92 to detect the predicted memantine effects; with maximum expected attrition (n=24), power is 0.85. Past findings also lead to the prediction that these MEM effects would be most robust in subjects exhibiting the lowest basal PPI levels (d=1.80). Using a median split of mean basal (screening) PPI levels, ANOVA as above will detect a significant interaction of memantine dose x basal PPI level, or dose x basal level x int, and significant post-hoc comparisons at one or more prepulse intervals (again, 120 ms being the strongest *a priori* candidate). Given the published "d" in control subjects, a comparable "d" in the proposed 12-15 "low PPI" patients/dose group would yield power >0.95 to detect the predicted memantine effects.

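### Testing basal PPI as a moderator by median split, with no continuous analysis planned, gives up power whenever moderation is graded; the loss is conditional, about 0 to 23 points

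*Protocol*

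**What the plan says.** Protocol section 9.j plans a repeated-measures ANOVA of PPI with memantine dose and prepulse interval as within-subject factors. It predicts the largest effects in patients with the lowest basal PPI, citing d=1.80 from earlier work in controls, and then states: "Using a median split of mean basal (screening) PPI levels, ANOVA as above will detect a significant interaction". The terms it names are the two-way interaction between dose and basal level and the three-way term that adds prepulse interval. Post-hoc comparisons follow, with 120 ms as the leading a priori interval.

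The power statements around it are:

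- Overall effect: "The effect size (d) for PPI-enhancement by 20 mg memantine in HCS was 0.91"; on that basis "30 patients/dose yields power of 0.92 to detect the predicted memantine effects", and "with maximum expected attrition (n=24), power is 0.85".
- Low-PPI half: "a comparable 'd' in the proposed 12-15 'low PPI' patients/dose group would yield power >0.95 to detect the predicted memantine effects".

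The same section says that the two dose groups are analysed separately. The low-PPI count of 12 to 15 is half of 24 to 30, so the cut appears to be made within each dose group. No power is given for the dose by basal PPI interaction. The SAP does not mention basal PPI as a moderator.

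**The concern.** Screening PPI is measured on a continuous scale. After a median split, two patients just either side of the median count as fully different, while the most extreme and the mildest patient in the same half count as identical. If the response to memantine changes gradually with basal PPI, the variation within each half goes into the error term and the interaction becomes harder to detect. With 24 to 30 patients per dose there is little power to spare.

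There is also a problem of use. Protocol section 8 hopes to identify in advance the patients in whom memantine helps, and names low basal PPI among the candidate markers. A sample median gives no threshold that carries over to a new patient, and it can differ between the 10 mg and 20 mg groups. Protocol section 9.e defines high and low PPI in another way, by quartiles of a normal population. A slope would give a predicted drug effect at any screening value.

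**Working it through.** **1. The plan's own figures.** Inputs are from protocol section 9.j: d=0.91 with n=30 or 24, d=1.80 with n=12 to 15, and alpha 0.05 (sidedness not stated; taken as two-sided). In the two-sample form, with noncentrality d×√(n/2) and 2n−2 degrees of freedom:

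| d | n | Recomputed | Stated |
|---|---|---|---|
| 0.91 | 30 | 0.934 | 0.92 |
| 0.91 | 24 | 0.870 | 0.85 |
| 1.80 | 12 | 0.988 | >0.95 |
| 1.80 | 15 | 0.997 | >0.95 |

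The first two agree within 2 points and the last two are consistent with the claim. A paired form, with noncentrality d×√n, would give 0.998 and 0.989 at d=0.91, so the protocol appears to have used the two-sample convention. All these figures concern a drug effect, overall or within the low half. None concerns the interaction.

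**2. Information kept by the split.** For a normal moderator with a linear effect, a median split keeps 2/π = 0.637 of the information on the slope. Then 30 × 0.637 ≈ 19 patients. In large samples, continuous-analysis power of 0.80, 0.90 or 0.95 falls to 0.61, 0.73 or 0.82.

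**3. Power at the planned sizes.** Simulation of the drug-minus-placebo PPI change against screening PPI (linear effect, normal moderator, two-sided 5%, at least 20,000 runs per setting). Here r is the correlation between screening PPI and the change. It is an assumption; the documents give no value.

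| n | r | Continuous | Median split | Loss (points) |
|---|---|---|---|---|
| 30 | 0.3 | 0.38 | 0.26 | 12 |
| 30 | 0.4 | 0.61 | 0.41 | 20 |
| 30 | 0.5 | 0.83 | 0.62 | 21 |
| 30 | 0.6 | 0.96 | 0.80 | 16 |
| 30 | 0.7 | 0.99 | 0.94 | 6 (unrounded values) |
| 24 | 0.41 | 0.54 | 0.35 | 18 (unrounded values) |
| 24 | 0.5 | 0.73 | 0.50 | 23 |

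Both tests hold 5% at r=0.

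**4. Anchoring to the protocol's effect sizes.** If the low half has d=1.80 and the whole group 0.91, equal halves imply 2×0.91 − 1.80 = 0.02 in the high half, a gap of 1.78. For a linear effect the slope per SD of screening PPI is 1.78 / (2√(2/π)) = 1.78/1.596 ≈ 1.12. In units of the single-session SD, the residual variance of the change is 2(1−c), where c is the placebo/active correlation, which is not stated. The implied correlation between moderator and change is then 1.12/√(1.12² + 2(1−c)).

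| c | Implied r | n=30: continuous vs split | n=24: continuous vs split |
|---|---|---|---|
| 0 | 0.62 | 0.97 vs 0.84 | 0.92 vs 0.73 |
| 0.25 | 0.67 | 0.99 vs 0.91 | 0.97 vs 0.83 |
| 0.5 | 0.74 | 1.00 vs 0.97 | 0.99 vs 0.93 |
| 0.7 | 0.82 | 1.00 vs 1.00 | 1.00 vs 0.98 |

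The loss is about 13 and 19 points (n=30 and n=24) at c=0, 3 and 7 at c=0.5, and 0 and 2 at c=0.7. If d is already expressed in SDs of the change score, it is 0 and 1.

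**5. A weaker interaction.** With half that gap (0.89) and c of 0, 0.25, 0.5 and 0.7, the loss is 18, 21, 22 and 17 points at n=30, and 15, 19, 22 and 21 at n=24.

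**6. Other shapes.** With a uniform moderator the loss peaks at about 16 to 17 points; with a strongly skewed (exponential) one, at about 30. If the true effect is a step exactly at the median, the split is better by up to about 9 points.

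**The case against.** The strongest objection is that linearity drives the result and the documents do not establish it. The protocol predicts only that the effect is greatest where basal PPI is lowest, which a threshold also fits. Carrying the 1.78 gap over as a straight line gives predicted d of 0.91 − 1.12 ≈ −0.2 at one SD above the mean and 0.91 − 2.23 ≈ −1.3 at two SD. Memantine would then reduce PPI in high-PPI patients, which this part of the protocol does not predict. This stands, and it is why the loss must be stated as conditional and linearity checked.

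Second, the design is within-subject, so a positive placebo/active correlation is likely, and at the protocol's own gap both analyses then approach full power. That also stands. However, it assumes that the moderation seen in healthy controls carries over to patients undiminished. At half the gap the loss is 15 to 22 points at every correlation tried.

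Third, the planned ANOVA includes prepulse interval, whereas the simulation uses one change score. A replacement that reduced the analysis to one change score would drop the planned three-way test, so the fix has to keep it.

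A reader might also infer more than the documents support:

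- That the split costs a fixed number of points. It does not: the change-score SD, the placebo/active correlation and the distribution of screening PPI are all missing.
- That the stated power above 0.95 is wrong. It concerns the drug effect in "12-15 'low PPI' patients/dose group" and it reproduces.
- That a median split is the poorest choice available. Under the same model a 75/25 split keeps only about 54%.
- That the trial's leading biomarker is at stake. Aim 3 names only genotype as moderator for patients, and section 9.j calls COMT genotype critical; basal PPI is one of several markers.

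**Conclusion.** The point holds as a conditional loss of efficiency in a secondary moderator test. The plan dichotomises a measured continuous moderator in dose groups of 24 to 30 and offers no continuous analysis. Under linear moderation and a normal moderator, the split keeps about 64% of the information. The power loss then runs from about 0 to 23 points: about 18 to 23 for moderate interactions (assumed r of 0.4 to 0.5), and little or none when the interaction is very strong. A marked skew in screening PPI could raise the maximum to about 30 points; a true step at the median would reverse the sign, by up to about 9.

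The primary test of memantine on PPI and its sample size do not depend on the split, and no stated figure is shown to be wrong. The change is worth making because a continuous analysis uses data already collected and does best where a real moderator is most easily missed.

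**What to change.** In protocol section 9.j, replace the median-split factor with centred screening PPI as a continuous covariate in the planned repeated-measures model, separately for each dose group. Keep both planned terms: dose by basal PPI, and dose by basal PPI by prepulse interval. An equivalent form is to regress the drug-minus-placebo change in PPI on screening PPI twice, once for the change averaged over intervals and once at the a priori 120 ms interval.

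Report the slope with its 95% confidence interval and the predicted drug effect at a low and a high screening value. Check linearity with a residual plot. Keep the median split for display only.

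The SAP omits this moderator and reports its analyses as completed, so the continuous analysis should be labelled as added.

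The cost is wording and a re-run on existing data. The downside is the assumed linear form: if the response really changes in a step near the median, the continuous test would be somewhat less powerful than the split.

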j. Statistics: Tests for homogeneity of variance are performed, and if appropriate, analyses of variance (ANOVA) used. Statview/Superanova software is used on the Macintosh. For startle data, P-Alone amplitude, PPI and startle latency are analyzed by ANOVAs; for drug studies, drug dose is used as a within-subject factor. Habituation is detected by a significant effect of trial block. Visuospatial priming is analyzed separately for baseline, facilitation, and inhibition conditions using ANOVAs. Baseline is a measure of visuospatial response time, while facilitation and inhibition scores are measures of sensorimotor modulation. Nonparametric statistics are used for the Latent Inhibition analyses because data from this test tend toward a bimodal distribution. A rank sum factorial analysis is used for the data. Other dependent measures will be analyzed with parametric or non-parametric analyses, generally consisting of mixed design ANOVAs, as appropriate. Following a significant ANOVA, specific comparisons are made using Tukey's tests. Alpha is 0.05.

Power considerations: Sample sizes vary across the different studies, based on issues ranging from the study design and goals to empirical evidence for effect sizes with the proposed drug or measure. For example, "ONE-DAY" studies are designed to identify and "pilot" optimal stimulus parameters for testing specific hypotheses, and these studies may not be powered to achieve traditional levels of statistical significance. On the other hand, designing studies of drug effects on PPI and related measures in control or patient populations requires detailed power information.

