Lastly, based on the impact of basal PPI level and personality measures in controls, we hypothesize that a critical moderating factor underlying PPI memantine sensitivity is COMT Val158Met genotype; specifically, we predict that "Val/Val" individuals will be most sensitive to memantine-enhanced PPI. This will be tested in two ways: first, by ANOVA as above, with COMT status as a between-subject factor, and memantine dose and prepulse interval as within-subject factors. Significant genotype x dose or genotype x dose x int interactions, with appropriate post-hoc comparisons, would confirm the hypothesis. Estimating d=1.53, based on the mean "d" of two "COMT phenotypes" in controls - low basal PPI (d=1.80) and high "novelty seeking" personality (d=1.27) - the proposed 11 Val/Val and 7 Met/Met patients/dose group would yield power of 0.90 to detect genotype-sensitive memantine effects. It is possible that various factors (including a skewed distribution of allele frequencies, or substantial genotype effects on basal PPI levels) might preclude detection of a significant 2- or 3-way interaction. A secondary (albeit weaker) test of the hypothesis will utilize separate ANOVAs in Val/Val vs. Met/Met subgroups, with predicted PPI-enhancing effects of memantine in the Val/Val but not Met/Met subgroups. Previous reports also predict a significant main effect of genotype, with PPI levels following the Met/Met>Val/Met>Val/Val gradient. Logistic regressions might be used, with genotype coded to reflect "dose" of the Met allele (Val/Val=0, Val/Met=1, and Met/Met=2), to assess the distribution of the neurophysiological and neurocognitive measures. All analyses will be conducted independently for each dose group. If comparable effects are evident with 10 and 20 mg doses, dose groups may be pooled to increase power for exploratory analyses (e.g. to detect genotype x drug effects).

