Main effects of memantine on WM will be tested by one-way ANOVA with memantine dose as a withinfactor. Based on d=0.73 for increased WM after 20 mg MEM in controls (see above), the proposed 30 patients/dose group would yield power of 0.79 to detect significant WM-enhancing effects. While preliminary data yield less robust predictions for COMT subgroup sensitivities in memantine effects on WM performance, given the significant correlation of WM and PPI, and known impact of COMT genotype on PPI levels, we predict some differential (Val/Val > Met/Met) memantine sensitivity in this measure. If we estimate effects of COMT status on WM memantine-sensitivity to be comparable to those for PPI (65% increase in effect size), then the estimated d for Val/Val vs. Met/Met sensitivity should be 1.20, and the proposed genotype subgroup sizes would yield power of 0.65 to detect genotype-sensitive memantine effects on WM.

Secondary "biomarkers" are MMN and GBS. For MMN, positive memantine effects will be detected by increased MMN amplitude at electrode Fz. For GBS, positive memantine effects would be detected by increased 40 Hz evoked power at electrode Fz. Unlike those for PPI, predictions of positive memantine effects on MMN and GBS are not based directly on previous findings from our laboratory, using measures identical to those proposed herein. However, based on reports in healthy subjects from other laboratories of memantine effects on MMN (d=0.87) and ketamine effects on GBS (d=0.69), the proposed 30 patients/dose group would yield power of 0.90 and 0.75, respectively, to detect positive memantine effects on these measures.

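### The COMT and basal-PPI moderator hypotheses can each be confirmed by either of two interactions, analysed separately in two dose groups at 0.05, and no rule says which interaction or dose group decides

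*Protocol*

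**What the plan says.** All the relevant text is in Protocol Section 9, item j (Statistics and Power considerations). Within a dose group, the protocol's dose factor means active drug against placebo.

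- COMT: the predicted pattern is greatest sensitivity in Val/Val patients. The rule is: "Significant genotype x dose or genotype x dose x int interactions, with appropriate post-hoc comparisons, would confirm the hypothesis".
- Basal PPI, by median split: "ANOVA as above will detect a significant interaction of memantine dose x basal PPI level, or dose x basal level x int". The same sentence also asks for "significant post-hoc comparisons at one or more prepulse intervals (again, 120 ms being the strongest *a priori* candidate".
- Dose groups: "All analyses will be conducted independently for each dose group".
- Error control: "Following a significant ANOVA, specific comparisons are made using Tukey's tests. Alpha is 0.05".
- Pooling: if the two doses behave alike, "dose groups may be pooled to increase power for exploratory analyses (e.g. to detect genotype x drug effects".
- Working memory: "we predict some differential (Val/Val > Met/Met) memantine sensitivity in this measure". No rule for confirming this prediction follows.

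Separate ANOVAs within the Val/Val and Met/Met subgroups are described as a weaker, secondary test. The SAP mentions neither COMT nor basal PPI, so it adds no control. Its PPI, MMN and ASSR paragraphs each report that the hypothesis was confirmed at 20 mg.

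**The concern.** Each moderator hypothesis has two interaction terms that can confirm it, and each term is tested in two separate groups of patients. That makes up to four tests at 0.05 per hypothesis. Tukey's procedure acts inside one ANOVA that is already significant. It does not cover the choice between the two-way and three-way term, or between the dose groups.

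This matters because Sections 7 and 8 of the protocol want these results in order to identify in advance which patients are likely to gain. The subgroups are small: 11 Val/Val and 7 Met/Met patients per dose group, and 12-15 low-PPI patients. If memantine helped everyone equally, a false moderator finding would wrongly divide patients into sensitive and insensitive groups.

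**Working it through.** **Inputs from the documents.** Alpha 0.05; two interaction terms per hypothesis; two dose groups of 30 different patients; 11 Val/Val and 7 Met/Met per group, which leaves 30 - 11 - 7 = 12 Val/Met; five prepulse intervals (SAP); d = 0.91 for memantine on PPI in controls.

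**Step 1: the plan's own figure.** The protocol gives power 0.90 for d = 1.53 with 11 against 7. The mean of 1.80 and 1.27 is 1.535. The standard error factor is sqrt(1/11 + 1/7) = 0.4835, and 1.53/0.4835 = 3.16. Then 3.16 - 1.96 = 1.20, and the normal approximation gives power 0.886. A one-sided noncentral t gives 0.916 and a two-sided one gives 0.844. So 0.90 is approximately reproduced as the power of one two-group comparison at 0.05. It makes no allowance for alternative tests.

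**Step 2: the interaction step, with no true moderation.**
- One dose group, two tests: 1 - 0.95^2 = 0.0975.
- Both dose groups, four tests: 1 - 0.95^4 = 0.185, and 0.185/0.05 = 3.7.

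Simulation gives 0.18-0.19 when sphericity holds. It gives about 0.21 with autoregressive correlation of 0.6 between intervals and no sphericity correction.

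**Step 3: adding the post-hoc comparison and the direction (COMT, both dose groups).** The protocol does not define the appropriate post-hoc comparison, so several readings were simulated. All correlations are assumptions.

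| Reading | Memantine has no effect | Memantine raises PPI equally in everyone |
|---|---|---|
| A. Two-way term in the predicted direction, plus active above placebo (p<0.05) at one or more intervals in Val/Val; for the three-way term, an interval significant in Val/Val but not in Met/Met | 3-4% | 10-13% |
| B. As A, with the interval comparisons corrected for five intervals (Bonferroni standing in for Tukey) | about 1% | 6-10% |
| C. Looser: either interaction, plus active above placebo at any interval in Val/Val, with the direction of the interaction not enforced | 4% | 14-21% |
| D. Either interaction, plus a Val/Val advantage over Met/Met (p<0.05) at one or more intervals | 7-8% | 7-8% |

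A and B use genotypes 11/12/7, exchangeable correlation (0.25-0.75 for A), and a standardised paired effect of 0.64 or 0.91 when the drug works. The value 0.64 is 0.91/sqrt(2), the paired effect if 0.91 is in single-day SD units and the two days are uncorrelated. C and D compare 11 with 7, with correlation 0.5 (exchangeable) or 0.6 (autoregressive) and an effect of 0.5 or 0.91 SD at each interval. For comparison, one pre-named directional COMT test in one dose group gives about 2-3%.

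**The case against.** The strongest reply is that the rule is more than a significant interaction. It also asks for supporting post-hoc comparisons, and the direction is predicted in advance. A reader might infer from the count of four tests that a false biomarker claim is about four times as likely as alpha allows. The documents do not support that: 3.7 times applies only before the post-hoc clause, and if memantine does nothing, readings A to C fall below alpha. This part of the objection stands, and it lowers the size of the concern.

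Other stronger readings also go too far:

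- **No hierarchy at all.** The subgroup ANOVAs are ranked secondary, pooling is called exploratory, and 120 ms is the favoured interval. However, none of this ranks the two interactions or the two dose groups, and 120 ms is favoured without being binding.
- **Success in either dose group is enough.** This is inferred from separate analysis and the lack of a combining rule. The SAP words its conclusions by dose. For a claim limited to one dose, the interaction-step figure is 9.75%.
- **COMT on working memory adds two more confirmatory tests.** The protocol calls the supporting data less robust, puts power at 0.65 and gives no confirmation rule, so these tests should not be counted.
- **Both moderators form one family.** Eight independent tests would give 1 - 0.95^8 = 0.337. But the protocol states two hypotheses and treats low basal PPI as a COMT-related phenotype, so neither the single family nor full independence is given.

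What remains is that the plan uses the language of confirmation and attaches power figures to these tests, yet leaves open which interaction, which dose group and which post-hoc comparison decide.

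**Conclusion.** The concern holds in this limited form. The either/or rule, applied separately in two dose groups, does not hold the stated 0.05. The figure of 18.5% per hypothesis is an upper one: it assumes sphericity, counts the interaction step alone and lets either dose group suffice. Under the predicted direction and a supporting post-hoc test, the false COMT claim rate is about 10-13% (about 6-10% with interval correction) when memantine helps everyone equally. That is the case that matters most, because the protocol expects memantine to raise PPI. With no drug effect the rate is about 1-4%, so the rule is not inflated in every situation. The range turns on a post-hoc condition that the plan leaves undefined. The defect lies in how the moderator claims are specified. It says nothing against the main memantine effect on PPI.

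**What to change.** In Protocol Section 9, item j:

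1. For each moderator, name the two-way moderator x drug interaction on PPI as the single deciding test, in one named dose group. The 20 mg group is the natural choice for the analysis, because it supplied the control-subject effect sizes. This is no view on dosing.
2. Define the post-hoc comparison that must accompany it: the interval or intervals, the correction and the direction.
3. If COMT and basal PPI both stay confirmatory, apply Holm across the two tests.
4. Label as exploratory the three-way terms, the other dose group, the separate-subgroup ANOVAs, the pooled analysis and COMT on working memory. Report them with estimates and confidence intervals.
5. Tie the statement that the hypothesis is confirmed to the named test alone.

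The SAP already reports 20 mg results and names no moderator test. A moderator test added there now would not be prospective and should be labelled exploratory (post hoc).

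**Cost.** The change is to wording only, with no new patients or data. Findings from the three-way term or the other dose group could no longer be called confirmed. Under Holm the smaller p-value must be below 0.025; if COMT has to meet that level, its power at d = 1.53 with 11 against 7 (two-sided noncentral t) falls from 0.84 to 0.75. Splitting alpha four ways instead (0.0125 each, familywise 1 - 0.9875^4 = 0.049) would cut it to 0.64, so naming one test is the cheaper remedy.

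### The PPI genotype power of 0.90 and the working-memory genotype power of 0.65, stated for the same 11 Val/Val and 7 Met/Met patients, do not fit together; the test that gives 0.65 gives about 0.84 for PPI

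*Protocol*

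**What the plan says.** Protocol section 9.j (Statistics, power considerations) sets alpha at 0.05 and gives two powers for a genotype-by-memantine effect in schizophrenia patients, analysed separately in each dose group.

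- **PPI.** The effect size is d = 1.53, the mean of two drug effects seen in control subgroups thought to resemble the Val/Val genotype: 1.80 (low basal PPI) and 1.27 (high novelty seeking). With this, "the proposed 11 Val/Val and 7 Met/Met patients/dose group would yield power of 0.90 to detect genotype-sensitive memantine effects".
- **WM.** The overall effect of 0.73 is raised by 65%; "then the estimated d for Val/Val vs. Met/Met sensitivity should be 1.20". On this basis "the proposed genotype subgroup sizes would yield power of 0.65 to detect genotype-sensitive memantine effects on WM".

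The second statement refers back to the same 11 and 7 patients. The section does not say which test was used for the power calculations, whether it was one- or two-sided, in what SD unit d is expressed, or what active–placebo correlation was assumed. It gives no reason for a different basis in the two calculations. The SAP contains no power calculation and does not mention genotype or WM.

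**The concern.** With the same patients and the same alpha, the only stated input that differs between the two power figures is d. An increase in d from 1.20 to 1.53 looked too small to lift power from 0.65 to 0.90.

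Genotype moderation of the memantine effect is named in Specific Aim 3, so a null genotype-by-dose result will be read against the stated power. At 0.90, such a result carries a 10% chance of having missed the assumed effect. If the true figure is nearer 0.84, that chance is about 16%, and the plan overstates how informative a null result would be.

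**Working it through.** **Inputs (Protocol 9.j).** Alpha 0.05; n1 = 11 Val/Val, n2 = 7 Met/Met; d = 1.53 (PPI) and 1.20 (WM); stated powers 0.90 and 0.65.

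**Step 1: reproduce the stated figures.** For a two-sample t-test, the noncentrality is ncp = d × √(n1·n2/(n1+n2)) = d × √(77/18) = d × 2.068, with 11 + 7 − 2 = 16 degrees of freedom and two-sided critical value 2.120.

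- WM: ncp = 1.20 × 2.068 = 2.482, power 0.645 (stated 0.65). With unrounded d = 0.73 × 1.65 = 1.2045, power is 0.648.
- PPI: ncp = 1.53 × 2.068 = 3.164, power 0.844 (stated 0.90). With unrounded d = (1.80 + 1.27)/2 = 1.535, power is 0.846.

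Simulation gave 0.645 and 0.843. So the WM figure reproduces and the PPI figure does not. Power 0.90 with 11 and 7 patients would need d of about 1.67.

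**Step 2: try other tests.**

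| Test, 11 vs 7 | PPI, d = 1.53 (stated 0.90) | WM, d = 1.20 (stated 0.65) |
|---|---|---|
| Two-sided t, df 16 | 0.844 | 0.645 |
| Two-sided t, error df 27 (three genotypes) | 0.862 | 0.667 |
| Two-sided normal approximation | 0.886 | 0.699 |
| One-sided t, df 16 | 0.916 | 0.767 |
| One-sided normal approximation | 0.936 | 0.799 |

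Within 2 points, each stated figure can be matched alone, but no row matches both. A search over two-group sizes from 3 to 30 and paired sizes from 3 to 30, one- and two-sided, found no t-test that gives both.

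**Step 3: a check that does not depend on group sizes or the SD unit.** If these are common to both measures they cancel, and the ratio of the noncentralities must equal the ratio of the d values.

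- Two-sided t, df 16: power 0.90 needs ncp 3.455 and power 0.65 needs 2.497, so the ratio is 3.455/2.497 = 1.384. It is 1.383 at df 27 and 1.382 for the normal approximation. Allowing ±0.005 on each stated power, the range is 1.36 to 1.40.
- One-sided: ratio 1.44, range 1.42 to 1.47.
- The plan's ratio: 1.53/1.20 = 1.275. Allowing for rounding of d, at most 1.535/1.195 = 1.285.

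The plan's ratio lies below both ranges. If d is rescaled equally for both measures so that PPI reaches 0.90, WM comes to 0.72; if WM is set at 0.65, PPI comes to 0.85.

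**Step 4: which figure is the outlier?** The same two-sided two-sample formula, with equal groups of the stated size, was applied to the plan's five other point-value powers.

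| Comparison | d | n | Stated | Formula |
|---|---|---|---|---|
| PPI main effect | 0.91 | 30 | 0.92 | 0.934 |
| PPI main effect, maximum attrition | 0.91 | 24 | 0.85 | 0.870 |
| WM main effect | 0.73 | 30 | 0.79 | 0.794 |
| MMN | 0.87 | 30 | 0.90 | 0.912 |
| Gamma band synchronization | 0.69 | 30 | 0.75 | 0.748 |

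All five are within about 2 points, as is the WM genotype figure. The PPI genotype figure is about 6 points away. This shows fit, not a documented method: these five comparisons are within-subject, and a paired test with d in change-score SD units would give 0.998, 0.989, 0.971, 0.996 and 0.955.

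**The case against.** The strongest reply is that the two powers need not be for the same test. For PPI the plan describes a mixed ANOVA with prepulse interval as a further within-subject factor, and accepts either a genotype-by-dose or a genotype-by-dose-by-interval interaction. WM has no interval factor. If the two-way test has power 0.844 and the three-way test were independent with power of about 0.36, the chance that at least one succeeds would be 1 − 0.156 × 0.64 = 0.90, with WM unchanged. This is possible, but the Protocol does not say that 0.90 was obtained this way. It also does not explain the pattern: the PPI main-effect powers come under the same interval factor and the same either/or rule, yet "30 patients/dose yields power of 0.92 to detect the predicted memantine effects" and "with maximum expected attrition (n=24), power is 0.85" lie slightly below the simple formula (0.934 and 0.870), not above it.

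A second reply is that different active–placebo correlations could reconcile the pair. If d is in raw-score SD units, dividing it by √(2(1 − r)) converts it to change-score units; r of about 0.58 for PPI and 0.51 for WM would give 0.90 and 0.65. The difference is small, but the documents give no correlation for either measure. This stands as a reason to let the authors document another method, and as a reason to call 0.84 conditional.

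It is also fair that the consequence is limited. No sample size rests on this figure, section 9.j already warns that the interaction may go undetected, and the plan's own inputs of 1.27 and 1.80 give powers of 0.69 and 0.94 by this test, a wider spread than the gap at issue. A null genotype result should in any case be read mainly from its estimate and confidence interval. These points limit the weight of the finding but do not make the two figures agree.

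**Conclusion.** The concern holds. On any common two-group basis, 0.90 and 0.65 cannot both be right for d = 1.53 and d = 1.20 in the same patients. By the test that yields the WM figure, PPI genotype power is about 0.84, so the stated value is about 6 points too high.

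The 0.84 assumes a two-sided alpha of 0.05 and that d is the standardised Val/Val minus Met/Met difference in memantine response, which is how the Protocol words it for WM. The inconsistency itself needs only that group sizes, sidedness and SD unit are shared by the two calculations.

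A related, lesser point: 1.53 is an average of drug effects within sensitive subgroups, so using it as the difference between genotypes assumes essentially no memantine effect in Met/Met patients. The plan does expect this ("predicted PPI-enhancing effects of memantine in the Val/Val but not Met/Met subgroups") but does not state it as a condition of the power figure.

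This is a correction to a stated power and to how a null genotype result is read, not a flaw in the design.

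**What to change.** In Protocol section 9.j, do one of the following:

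1. Restate the PPI genotype power as about 0.84, by the same test as the WM figure of 0.65, and name the test, its sidedness and the SD unit of d.
2. If another method or correlation produced 0.90, state it, and either recompute the WM figure by that method or justify the different input.

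In either case, add a sentence that using d = 1.53 as the genotype contrast assumes essentially no memantine effect in Met/Met patients.

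The cost is Protocol wording and possibly a less favourable stated power. No new patients are needed.
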